5.1.2 Disposition by investigator site

An overview of the date of first study participant in (earliest EV), date of last study participant out (latest scheduled or unscheduled visit), and the number of screened study participants will be summarized for all study sites, individual study site, and country.

Additionally, the number of study participants in the SS and PKAS will be summarized for all study sites, individual study site, and country.

5.1.3 Discontinuation due to AEs

The number and percentage of study participants who discontinued the study due to an AE will be summarized for the SS. Discontinuation due to AEs will be classified as serious fatal, non-fatal, and other (non-serious fatal). If a participant has multiple AEs that lead to discontinuation, the most severe type will be summarized.

5.2 Protocol deviations

The number and percentage of study participants with at least 1 IPD will be summarized overall and by main category of protocol deviation. Specific categories of protocol deviations will be defined within IPD documentation.

In addition, IPDs will be listed.

5.3 COVID-19

All data collected from the COVID-19 Impact eCRF page will be listed.

6 DEMOGRAPHICS AND OTHER BASELINE CHARACTERISTICS

Demographic and Baseline characteristics will be summarized and listed for the SS unless otherwise stated.

6.1 Demographics

All demographic data collected at the EV in EP0132 will be summarized. The data sources for the EP0132 EV are detailed in [Section 3.3.6](#). In addition, the weight, height, and BMI of the study participant at Baseline in N01269 will be summarized using data from the N01269 analysis database.

Tables with descriptive statistics will be provided for the following demographic variables:

- Continuous and categorized age at EV
 - Age categories: 2 to <4 years, 4 to <6 years, 6 to <12 years, 12 to <19 years, 19 to 25 years, <18 years
 - Categorized age in years for EudraCT and clinicaltrials.gov reporting
- Gender
- Race
- Ethnicity
 - Hispanic or Latino / Not Hispanic or Latino
- Countries
- Continuous and categorized weight at EV and at N01269 Baseline
 - Weight categories: <50kg, \geq 50kg
- Height at EV and at N01269 Baseline
- Continuous and categorized BMI at EV and at N01269 Baseline
 - BMI categories: \leq 13.5 kg/m², 13.5 to 30 kg/m², \geq 30 kg/m²

The summaries for demographic characteristics will be conducted on the SS.

Demographic characteristics will be listed for the ASPS Set.

No tables will be presented for childbearing potential/birth control. A study participant data listing for the ASPS Set will be produced for female participants and will include reproductive potential, whether the participant is sexually active, and method of birth control.

6.2 Other Baseline characteristics

In all sections below the date of absence seizure diagnosis is obtained from the analysis database for N01269. For participants with a partial date of absence seizure diagnosis in N01269, the imputed date of absence seizure diagnosis in N01269 will be used in EP0132. In all sections below “EV” refers to the EV in EP0132.

6.2.1 History of epileptic seizures

History of epileptic seizures will summarize absence epilepsy duration in both years and months, age at time of absence seizure diagnosis in both years and months, and percent of life with absence epilepsy for the SS. A listing reflecting absence epilepsy duration in both years and months, age at time of absence seizure diagnosis in both years and months, and percent of life with absence epilepsy relative to the date of absence seizure diagnosis will be provided for the SS.

6.2.1.1 Absence epilepsy duration

Absence epilepsy duration is the number of years and months from the date of diagnosis of absence seizures to the date of EV in EP0132. If absence epilepsy duration is greater than the study participant's age due to the application of the imputation rules for date of absence seizure diagnosis in N01269, then epilepsy duration is set equal to the study participant's age.

6.2.1.2 Age at time of absence seizure diagnosis

Age at time of absence seizure diagnosis will be calculated in both years and in months using the following formula:

Age at absence seizure diagnosis (years) = [(Age at EV in months – Number of months between EV and date of diagnosis)/12].

Age at absence seizure diagnosis (months) = (Age at EV in months – Number of months between EV and date of diagnosis).

Where number of months between EV and diagnosis = [(Date of EV – date of diagnosis)/30].

For these calculations, it is assumed there are 30 days in a month. Only complete months and years will be considered in the calculation of age at absence seizure diagnosis, ie, if age at absence seizure diagnosis is calculated as 3.2 years then this will be assumed to be 3 years.

6.2.1.3 Percent of life with absence epilepsy

Percent of life with absence epilepsy will be calculated as 100 times absence epilepsy duration (in months) divided by the study participant's age in months at EV.

6.3 Medical history, procedure history, and concomitant medical procedures

Medical history, procedure history, and concomitant medical procedures will be reported as collected on the EP0132 eCRF only – no integration of data from the N01269 analysis database will be performed. Ongoing conditions that initially occurred after the time of entry into N01269 will be recorded as an AE, not as medical history on the EP0132 eCRF. Only conditions that occurred prior to N01269, that were not captured in N01269 database, should be entered as medical history on the EP0132 eCRF.

Listings of medical history conditions and glossary for the SS will be provided.

Procedure history and concomitant medical procedures will not be summarized. Listings of procedure history and concomitant medical procedures will be provided, based on the SS.

6.4 Previous and concomitant medications

Medications will be summarized as reported on the EP0132 eCRF without integration of medications from the N01269 analysis database. Any medications that are ongoing at the time of entry into EP0132 will be entered on the EP0132 Concomitant Medications eCRF.

Medications will be classified into the following categories:

- Previous medication: includes any medications that ended prior to the first dose of study drug in EP0132
- Concomitant medication: includes any medications with at least one day in common with study treatment in EP0132 (including down-titration)
 - Includes medications that started prior to the first dose of study drug in EP0132 and continued after
 - Includes medications that started during treatment in EP0132
- Follow-up medication: includes any medications that started after the final dose of study drug in EP0132. Final dose of study drug includes down-titration medication, therefore follow-up medications are those with a start date during the Safety Period.

The number and percentage of study participants taking previous and concomitant non-AED medications will be summarized overall, and by anatomical main group (Anatomical Therapeutic Chemical [ATC] classification level 1), therapeutic subgroup (ATC classification level 2), and preferred drug name for the SS. Study participants reporting multiple medications within an ATC class are counted once per medication and class.

The number and percentage of study participants who took previous and concomitant AEDs, including benzodiazepines, will be summarized by preferred drug name for the SS.

The identification and classification of medications as AED, including benzodiazepines, will be performed by merging an external physician-reviewed spreadsheet (which includes relevant flags for selecting AED medications or benzodiazepines) with the data entered into the study database in order to categorize the medications correctly for the tables.

For summarization, similar AEDs are grouped and summarized together under the following groups:

- Valproate
- Phenobarbital
- Phenytoin

The medications to be included in each of the above groups are also flagged in the spreadsheet referred to above. Combination AEDs are not considered for grouping.

All medications will be listed for the SS.

7 MEASUREMENTS OF TREATMENT COMPLIANCE

Compliance will not be assessed due to the complexities associated with the calculation and interpretation of BRV compliance for this study.

8 EFFICACY ANALYSES

Unless otherwise indicated, all efficacy summaries and listings will be performed on the SS.

Scheduled and unscheduled locally read 1-hour EEGs will be listed, including if the EEG was performed, start and stop date and time of EEG, total number of interpretable EEG minutes while the study participant was awake, whether any seizures were observed during the EEG, ILAE seizure classification of any seizures that occurred, and the number of each seizure type.

Seizure diary data will be listed, including if the diary was completed, if any absence seizures occurred, if any non-absence seizures occurred, and the ILAE classification of any non-absence seizures that occurred.

8.1 Statistical analysis of the secondary efficacy variables

For all secondary efficacy variables, participants who continue in the study beyond 2 years will have their data truncated at the scheduled Month 24 YEV. Their post-Month 24 assessments visits will not be summarized in these analyses, however their 1-hour EEG and seizure diary data for these assessments will be listed.

8.1.1 Absence seizure freedom during the 1-hour EEG at each visit (including dropouts)

The number and percentage of study participants who are absence seizure free based on 1-hour EEG at each scheduled visit up to and including the scheduled Month 24 YEV or EDV (if prior to the Month 24 YEV) will be summarized. The Month 24 YEV may be the FV for some participants. The derivation of absence seizure freedom based on EEG is specified in [Section 3.13.2](#).

The number of study participants that discontinue the study prior to Month 24 that are imputed as not absence seizure free for all subsequent scheduled visits after the EDV will be summarized at each applicable visit. These participants will be summarized as a sub-category under not absence seizure free.

The number and percentage of study participants who met each individual criterion will also be summarized at each visit. Percentages for absence seizure free, not absence seizure free and Criterion 1 will be based on the number of participants in the SS as the denominator. Percentages for criteria 2, 3 and 4 will be based on the number of participants in the SS who met Criterion 1 at each visit.

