3.13.2 Absence seizure freedom during the 1-hour EEG (including dropouts)

The endpoint of absence seizure freedom on 1-hour EEG with no concomitant use of any AEDs, including benzodiazepines, within 4 days prior to or during the EEG will be assessed at each scheduled EEG visit up to and including the Month 24 YEV (or FV, if applicable) or EDV.

At each timepoint, a study participant is defined as absence seizure free if they meet all the following criteria:

1. 1-hour EEG was conducted on the study participant
2. Quality of 1-hour EEG while awake deemed sufficient for analysis
3. No absence seizure identified while awake on 1-hour EEG
4. No concomitant use of any AEDs, including benzodiazepines, on the day of initiating and during the 1-hour EEG or the 4 study days prior to it

Specific algorithmic rules for each of the above criteria are defined as follows:

Criterion 1: A study participant is defined as receiving the 1-hour EEG if there is a record that this test was conducted in the eCRF.

Criterion 2: The EEG is deemed of sufficient quality if at least 30 minutes of readable EEG while awake is recorded, as reported on the EEG eCRF.

Criterion 3: 1-hour EEG with no absence seizures recorded on the EEG eCRF (ILAE code IIA).

Criterion 4: No records of any concomitant AED, including benzodiazepines usage on the Concomitant Medications eCRF on the day of initiating the 1-hour EEG, or the 4 days prior to it.

Note that Criteria 2, 3 and 4 can only be assessed if Criterion 1 is met.

At each timepoint, if the study participant does not meet all the criteria for absence seizure freedom they will be regarded as not absence seizure free. If a participant discontinues the study early, prior to Month 24, they will be imputed as not absence seizure free for all subsequent scheduled visits after the EDV until Month 24. If a participant has a FV prior to the Month 24 assessment visit, they will not be included in any summaries for the scheduled visits following the FV.

In the event where multiple scheduled locally read 1-hour EEGs are recorded at the same timepoint, only the first EEG will be used for analysis, regardless of the quality of this EEG. The later EEGs will be considered as exploratory and listed only.

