If a study participant discontinues the study during a 3-month period then Criterion 1 will be checked based on the full 3-month period and if met, the participant will be assessed for absence seizure freedom in the period of discontinuation. If Criterion 1 is not met, absence seizure freedom status will be imputed as not absence seizure free for the period of discontinuation and all subsequent 3-month periods, ending at Months 22 to 24. Study participants who discontinue the study early will still be included in the analysis conducted on the Evaluation Period.

If a study participant has a FV during a 3-month period then Criterion 1 will be checked based on the full 3-month period and if met, the participant will be assessed for absence seizure freedom in the period of the FV. If Criterion 1 is not met, the participant will not be included in the summary for that period and all subsequent 3-month periods, ending at Months 22 to 24. Study participants who have a FV prior to the scheduled Month 24 YEV will still be included in the analysis conducted on the Evaluation Period.

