In each 6-month period, if the study participant does not meet all the criteria for absence seizure freedom they will be regarded as not absence seizure free.

In the event of an unscheduled EEG or an EEG performed at an EDV or FV that has not been mapped to a scheduled visit, if this EEG is on the same day as a scheduled visit this will be attributed in the analysis to the 6-month period of the scheduled visit. Otherwise, if this is not on the same day as a scheduled visit, this will be attributed in the analysis to the 6-month period of the following scheduled visit. For example, if an unscheduled EEG is performed between the Month 6 FEV and the Month 12 YEV, this will be considered in the analysis for the Month 12 YEV. As a further example, if an unscheduled EEG is performed on the same day as the Month 24 YEV, this will be considered in the analysis for the Month 24 YEV.

In the event of a missed scheduled visit any unscheduled EEG will be attributed to the period of time between the preceding visit and the next planned scheduled assessment visit relative to the EV, as defined in [Table 3-5](#). For example, if an unscheduled EEG is performed after the Month 9 MEV and the scheduled Month 12 YEV is missing, then the unscheduled Month 9 assessment will be considered in the analysis for the period from the day after the Month 6 FEV up to and including Day 365 (Protocol scheduled assessment day for Month 12 YEV).

If a participant discontinues early, their EEG performed at the EDV will be attributed to the 6-month periods of time following the preceding visit. For example, if an EDV is performed at Month 9 MEV, then the EDV assessment will be considered in the analyses for the periods from the day after the Month 6 FEV up to and including Day 365 (Protocol scheduled assessment day for Month 12 YEV). All subsequent 6-month periods for the participant will be regarded as not absence seizure free.

If a participant has a FV prior to the scheduled Month 24 YEV, their EEG performed at the FV will be attributed to the 6-month period of time following the preceding visit. For example, if a FV is performed at Month 9 MEV, then the FV assessment will be considered in the analyses for the period from the day after the Month 6 FEV up to and including Day 365 (Protocol scheduled assessment day for Month 12 YEV). The participant will not be included in the analyses for all subsequent 6-month periods.

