If a participant is regarded as absence seizure free at the scheduled FEV or YEV assessment (or at EDV) and absence seizure free at all unscheduled assessments since the last scheduled FEV or YEV assessment, then they will be regarded as absence seizure free in that 6-month period in the

consecutive analysis. If a participant is regarded as not absence seizure free at the scheduled FEV or YEV assessment (or at EDV) or at any unscheduled assessments since the last scheduled FEV or YEV visit, then they will be regarded as not absence seizure free for that 6-month period.

For the cumulative consecutive absence seizure freedom analysis, a study participant will be categorized as absence seizure free until the 6-month period in which they are first classified as not absence seizure free. After the recurrence of absence seizures, the participant is classified as not absence seizure free regardless of whether they met the criteria for absence seizure freedom in subsequent 6-month periods.

If a participant discontinues early, all subsequent 6-month periods for the participant are considered as not absence seizure free, regardless of their cumulative absence seizure status at the time of the EDV.

If a participant performs a FV prior to the Month 24 YEV and becomes not absence seizure free at any point prior to the FV then the participant will remain in the analyses for subsequent 6-month periods as not absence seizure free. However, if the participant performs a FV prior to the Month 24 YEV and they remain absence seizure free until the FV then they will remain in the analyses until the period of the FV, and will be excluded from the analyses for all subsequent 6-month periods.

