If a study participant discontinues the study during a relevant period then Criterion 1 will be checked and if met, the participant will be assessed for absence seizure freedom in the period of discontinuation. If Criterion 1 is not met, then the status will be imputed as not absence seizure free for that specific period and for all subsequent 6-month periods (where applicable), ending at Months 19 to 24.

If a study participant has a FV during a relevant period then Criterion 1 will be checked and if met, the participant will be assessed for absence seizure freedom in the period of the FV. If Criterion 1 is not met, then the participant will not be included in the analyses for that specific period and for all subsequent 6-month periods (where applicable), ending at Months 19-24.

For the cumulative consecutive absence seizure freedom analysis, a study participant will be categorized as absence seizure free until the 6-month period in which they are first classified as not absence seizure free. After the recurrence of absence seizures, the participant is classified as not absence seizure free regardless of whether they met the criteria for absence seizure freedom in subsequent 6-month periods.

If a participant discontinues early, all subsequent 6-month periods for the participant are considered as not absence seizure free, regardless of their cumulative absence seizure status at the time of the EDV.

If a participant performs a FV before the end of the Month 19-24 period and becomes not absence seizure free at any point prior to or at the FV then the participant will remain in the analyses for subsequent 6-month periods as not absence seizure free. However, if the participant performs a FV before the end of the Month 19-24 period, and they remain absence seizure free until the FV, then they will remain in the analyses until the period of the FV if they met Criterion 1 during the period of the FV, or the period prior if they did not meet Criterion 1 during the period of the FV, and will be excluded from the analyses for all subsequent 6-month periods.

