8.1.3 Absence seizure freedom based on diary (including dropouts)

The number and percentage of study participants who are absence seizure free based on diary will be summarized at 3-month time intervals within the Evaluation Period, as defined in [Table 3-3](#), and over the entire Evaluation Period truncated at the scheduled Month 24 YEV for participants who continue in the study beyond 2 years. The latter will additionally include any diary entries collected from the end of Months 22 to 24 up to the Month 24 YEV. The derivation of absence seizure freedom based on diary is specified in [Section 3.13.4](#).

Study participants who discontinue during or prior to each 3-month period and do not meet Criterion 1 are imputed as not absence seizure free for the period of discontinuation and all subsequent 3-month periods, ending at Months 22 to 24. These participants will be separately summarized as a sub-category of not absence seizure free in the summaries.

Similarly, study participants who discontinue during the Evaluation Period and do not meet Criterion 1 are imputed as not absence seizure free for the Evaluation Period; these participants will be summarized in a sub-category as described above.

The number and percentage of study participants who met each individual criterion will also be summarized. Percentages for absence seizure free, not absence seizure free and Criterion 1 will be based on the number of participants in the SS as the denominator. Percentages for criteria 2 and 3 will be based on the number of participants in the SS who met Criterion 1 at each visit.

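### Participants with a Final Visit before Month 24 are dropped from later seizure-freedom summaries, but the SAP keeps the whole Safety Set as the denominator

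*SAP*

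**What the plan says.** **Who is removed.** SAP 3.13.2 separates two kinds of leaver. Early discontinuers are imputed as not seizure free at each scheduled visit up to Month 24. Participants with an FV before Month 24 are taken out instead: "they will not be included in any summaries for the scheduled visits following the FV". The other derivations have their own FV rules:

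- Diary by 3-month period, 3.13.4 (and 3.13.6, which follows it with a 50% diary threshold): if diary completion (Criterion 1) is not met in the FV period, "the participant will not be included in the summary for that period and all subsequent 3-month periods".
- Consecutive EEG by 6-month period, 3.13.8: "The participant will not be included in the analyses for all subsequent 6-month periods".
- Consecutive diary by 6-month period, 3.13.9, for a leaver who fails Criterion 1 in the FV period: "then the participant will not be included in the analyses for that specific period and for all subsequent 6-month periods".
- Cumulative EEG, 3.13.8: a leaver who has already failed is kept ("then the participant will remain in the analyses for subsequent 6-month periods as not absence seizure free"), while one still free at the FV "will be excluded from the analyses for all subsequent 6-month periods". The cumulative diary rule in 3.13.9 makes the same split.

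**What the counts are divided by.** Section 8.1.1 gives one base for the seizure-free percentage and the two listed after it: "not absence seizure free and Criterion 1 will be based on the number of participants in the SS as the denominator". In 8.1.3 these percentages "will be based on the number of participants in the SS as the denominator". Sections 8.1.5, 8.1.6 and 8.1.7.1 name the same denominator, the first two for every summary in the section. None of the five mentions the FV exclusion. SAP 3.7.2 defines the SS by a single dose taken in this study, so nobody leaves it.

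**The concern.** The derivation sections take a participant out of the summary, and the reporting sections leave that participant in the denominator. No passage reconciles the two. Programmed literally, a completer with an early FV is counted below the line and in neither category above it. The seizure-free percentage falls at later visits because people completed and moved on, not because they had seizures. The efficacy tables in 8.1.1 and 8.1.3 have a sub-category for imputed early discontinuers but none for FV leavers, so a reader of those tables could not see the cause. Two programmers could also produce different percentages from the same data.

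**Working it through.** The plan states no figure for this point, so there is none to reproduce. The check sets the rules side by side and then works through assumed values.

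**1. Can an FV precede Month 24?** Yes. Protocol Table 1-2 lists the FV at Month 24 or later, but its footnote b gives an FV rather than an Early Discontinuation Visit to someone who leaves before Month 24 for another BRV study. Protocol 4.1 also specifies the FV for moves to managed access or commercial drug. SAP 3.3.5 sets no minimum time for completion, and 3.13.8 works through an FV at Month 9. Protocol 6.1 expects at least two years of treatment, so the case may be uncommon. No count is given.

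**2. Does another rule shrink the denominator?** SAP 3.2 has a default (participants with an assessment at the time point), but it yields where a section says otherwise, as these five do. Section 3.13.3 carries the same exclusion sentence as 3.13.2, and there 8.1.2 does write out a denominator of participants still ongoing.

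**3. Size on the literal reading.** Let f be the share of the SS excluded at a visit or period because of an FV, and p the seizure-free rate among those still included (early discontinuers counted as nonresponse). Reported rate = p(1 - f).

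| f (assumed) | p = 50% is shown as |
|---|---|
| 0% | 50% |
| 5% | 47.5% |
| 10% | 45% |
| 20% | 40% |
| 30% | 35% |

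At f = 10%, p = 40% is shown as 36% and p = 60% as 54%. With about 140 participants (SAP 2.4), each excluded leaver costs 100p/140 points: 0.29, 0.36 or 0.43 at p = 40%, 50% or 60%.

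EEG by visit with 14 leavers: 140 - 14 = 126 included, and 0.5 × 126 = 63 free. Literal: 63/140 = 45.0% free and 45.0% not free, a total of 90%. Reduced denominator: 63/126 = 50.0% each, a total of 100%.

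**4. Diary periods after the FV.** Exclusion from later periods is written only for leavers who fail Criterion 1 in the FV period. For those who meet it, 3.13.4 and the by-period part of 3.13.9 are silent. They could be counted as not free, since anyone not meeting all criteria in a period is so regarded. They could equally be outside the analysis, since the Evaluation Period ends at the FV (3.3.2) and, for adverse events, 3.3.3 counts a participant in a period only if the Evaluation Period reaches its first day. Section 3.13.5 settles the matter for its own analysis by excluding every period after completion.

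How many leavers this concerns depends on assumptions. With complete diaries, the 80% threshold and both day scales starting together:

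- FV evenly spread within 7 days of a scheduled Month 3 to 21 visit: 20 of 105 window days (19%) meet Criterion 1 for 3-month periods and 8 of 105 (8%) for 6-month periods.
- FV on any day of a period: 19/90 (21%) and 37/180 (21%).

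If 10% leave, p = 50% among those still followed, and 19% to 21% of leavers are counted as not free, correcting the denominator alone gives 0.45/(1 - 0.10 × 0.81) = 49.0% to 0.45/(1 - 0.10 × 0.79) = 48.9%, not 50.0%.

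**5. Whole Evaluation Period.** Section 3.13.4 keeps FV leavers in this summary, so 8.1.3 and 8.1.7.1 are consistent with the SS there. Section 3.13.9 is different: its criteria apply to a relevant period that can be the Evaluation Period, and an FV leaver who fails Criterion 1 in it is left out. Section 8.1.6 still divides by the SS.

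**6. Cumulative tables.** Let L be the share leaving at an FV and q the share of leavers still free then. With only the free leavers removed from the denominator, the rate is p(1 - L)/(1 - Lq). At p = 50%, L = 10%: 47.4% (q = 50%), 48.4% (q = 70%), 50% (q = 100%).

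**The case against.** The best defence is that leaving someone out of any summary naturally means out of both numerator and denominator, and that 8.1.1 points to 3.13.2 for its derivation. The ongoing denominator in 8.1.2 is needed anyway to remove early discontinuers, so it is weak evidence of what the authors intended in 8.1.1. That reading is possible, and it may be the intended one. It is not what the five reporting sections say, however, and naming a fixed set leaves the programmer to choose.

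It is also fair that an early FV is an exception to the schedule, that everything here is descriptive and single-arm with no testing, that the tables give counts, and that the disposition tables in SAP 5.1.1 show attendance by visit and period. In the EEG tables by visit the shortfall from 100% would be visible and could be recomputed. Section 8.1.2 reports the same endpoint without this conflict. These points limit the importance of the conflict but do not remove it.

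A reader might go further and infer that the SAP counts diary leavers who met Criterion 1 as not free in every later period. The documents do not support that as a rule; it is one of two readings of a silence. Nor do they show that the cumulative split is a mistake. A failure before the FV is already known and cannot be undone in that analysis, whereas continued freedom after the FV is unknown. Keeping the known failures is written deliberately and is debatable.

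**Conclusion.** The conflict is real and stands in the current SAP text. It affects the visit or period percentages for free, not free and Criterion 1 in 8.1.1, 8.1.3, 8.1.5, 8.1.6 and 8.1.7.1, and possibly the Evaluation Period summary in 8.1.6. Sections 8.1.2, 8.1.4 and 8.1.7.2 and the Evaluation Period results of 8.1.3 and 8.1.7.1 are free of it. It would be wrong to infer that every whole-period result is safe, because the rule that keeps FV leavers belongs to 3.13.4 and not to 3.13.9.

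The proportional loss equals f, which the documents do not give; the 0% to 30% range is an assumption, and at zero there is no effect. A reduced denominator describes those still included. It does not correct for responders leaving more often. The primary safety objective is untouched.

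**What to change.** 1. In 8.1.1, 8.1.3, 8.1.5, 8.1.6 (including its Evaluation Period summary) and 8.1.7.1, define the denominator as the SS minus participants whom the matching derivation section excludes at that visit or period because of an FV. For the diary this includes the FV period itself when Criterion 1 is not met. Keep early discontinuers in as nonresponse, and show the number excluded because of an FV in each table.
2. In 3.13.4 (and so 3.13.6) and the by-period part of 3.13.9, state that all periods after the FV period are excluded whether or not Criterion 1 was met, as 3.13.5 already does.
3. Leave the cumulative rule as it is, but note beside those tables that FV leavers who had already failed are kept and those still free are removed, so among FV leavers a reduced denominator retains only the failures.

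The cost is SAP wording and table programming; no new data or method is needed.
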